7.7.3.5.8 Quantitative Bias Analysis for MCMs

A sensitivity analysis will be conducted to quantify potential MCMs that might not have been included in the main analysis because the pregnancies resulted in elective termination, spontaneous abortion, or stillbirth rather than live births. A quantitative bias analysis will be conducted to evaluate the impact of elective termination, spontaneous abortion, and stillbirth on prevalence estimates for MCM.

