7.2.1.1.3 Infant Linkage

The identification of infant outcomes, such as MCMs or SGA birth, relies on data from the infant's claims record rather than the mother's claims record. Mother and infant records will be linked through the presence of a common unique family insurance identifier. This number is used by health plans to identify all members of a family who are covered by the same insurance plan for the purposes of defining coverage, payment, and reimbursement, providing assurance that mother-infant pairs identified in this manner are accurate. In addition, claim(s) relating to the delivery must be within 7 days of the infant's birth date (or 32 days for multiples). This linkage has been used to address regulatory questions by pharmaceutical companies about the effects of drugs on pregnancy (Carman et al., 2007; Wyszynski et al., 2016).

The fraction of identified deliveries that cannot be matched to an infant is likely due to the infant being covered under a different health insurance from the mother. This may occur if the newborn were to be added to the other parent's plan (rather than the mother's), if the parents were to switch from individual plans to family health plans, or if the mother were covered under her parents' policy (in which case a separate plan would need to be purchased for the infant).

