7.5 Study Size

Table 3 presents the minimum number of nemolizumab exposed pregnancies required to detect relative risks equal to or greater than 2.0, 2.5, or 3.0 for a comparative analysis of each of the study outcomes, assuming a ratio of 1:4 exposed to unexposed, 80% power, a 2-sided alpha of 0.05, and the referenced outcome prevalences. For infant outcomes, the minimum number of nemolizumab-exposed livebirths was calculated, and the number of nemolizumab-exposed pregnancies was derived from these counts based on the prevalence of live birth. For the primary outcome MCM, a study size of 214 live births with linked infants exposed to nemolizumab in the first trimester exposure window would provide an 80% power to detect a RR of 2.5, and 133 live births with linked infants exposed to nemolizumab in the first trimester exposure window would provide 80% power to detect a RR of 3. Assuming 80% of pregnancies have an observed outcome and 76% of observed outcomes are live births, an estimated 352 pregnancies exposed to nemolizumab during the first trimester would need to be accrued to detect a RR of 2.5 and 219 exposed pregnancies to detect a RR of 3. With a 1:4 ratio of exposed to unexposed, this corresponds to 1,408 pregnancies (for 2.5) or 876 (for 3) in each comparator group.

Table 3 Sample size required for 80% power to detect effect estimates for pregnancy and infant outcomes, with 1:4 matching¹

Outcome	Prevalence of Outcome	Relative Risk	Nemolizumab Exposed Pregnancies Needed	Nemolizumab Exposed Live Births Needed
MCM	3% ²	2	709	431
		2.5	352	214
		3	219	133
Ectopic pregnancy	1-2%	2	877	N/A
		2.5	438	
		3	275	
Elective termination	21%	2	45	N/A
		2.5	21	
		3	12	
Preterm birth, SGA birth	10% ^{3,4}	2	190	115
		2.5	94	57
		3	56	34
Spontaneous abortion	14% ⁵	2	77	N/A
		2.5	37	
		3	22	
Stillbirth	1% ⁶	2	1,324	N/A
		2.5	662	
		3	415	

Abbreviations: N/A, not applicable; SGA, small for gestational age

¹ Calculations were performed via www.OpenEpi.com using the Fleiss method, as described in Fleiss JL. Statistical Methods for Rates and Proportions. John Wiley & Sons, 1981.

² March of Dimes. Perinatal Data Snapshot: United States Birth Defects. 2015; http://www.marchofdimes.org/peristats/pdflib/999/pds_99_4.pdf.

³ Centers for Disease Control and Prevention. Quick Stats: Percentage of Small for gestational-Age Births, by Race and Hispanic Ethnicity—United States, 2005. MMWR. 2008;57(50):1359. <https://www.cdc.gov/mmwr/preview/mmwrhtml/mm5750a5.htm>.

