7.7.3.3 Comparative Analyses

Nemolizumab-exposed pregnancies will be matched to pregnancies in the two comparator groups in a 1:4 ratio based on maternal age at cohort entry, gestational week of dispensing, indication, and calendar week, separately within each data source. For all pregnancy and infant outcomes assessed at the end of pregnancy or during pregnancy, we will estimate RRs comparing the Nemolizumab Cohort to the comparator cohorts using robust Poisson regression models (for MCMs and SGA births) and HRs using Cox proportional hazards models (for all other outcomes). All comparative analyses will be performed incorporating stabilized IPTW to adjust for potential confounding. All analyses will be conducted by data source and then meta-analyzed (as described in [Section 7.7.3.4](#)).

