MCMs will be identified in live born infants, and study drug exposure will be assessed in the first trimester. However, the exact timing of the development of malformations is typically unknown. Additionally, while the use of ICD-10-CM Z3A codes to estimate LMP has been shown to be accurate ([Chomistek et al., 2023b](#)), not all pregnancies have Z3A codes, and some degree of measurement error is expected in estimating the beginning of pregnancy. The resulting exposure misclassification due to estimated LMP is not expected to be differential with respect to exposure. A sensitivity analysis will explore alternative exposure windows that are more conservative.

It is possible that selection bias may arise due to differential loss to follow-up (i.e., if pregnant women who receive nemolizumab are more or less likely to be lost to follow-up than those who are exposed to other AD/PN treatments or who are unexposed), though we expect censoring to be non-differential with respect to exposure and outcome status. To check this assumption, we will compare the baseline characteristics of pregnancies with an observed outcome versus those who were censored before the end of pregnancy. We will also describe the frequency of censoring events according to nemolizumab exposure status.

Residual confounding is always a concern in observational studies. While propensity score models can account for a large number of measured pre-specified and empirically derived variables, some variables may have a greater degree of misclassification, and some confounders may not be measured. For example, due to ICD-10 coding limitations, claims data tend to have incomplete capture of smoking status. However, the degree of residual confounding due to unmeasured factors may be reduced if proxies of unmeasured factors are included in the models ([Guertin et al., 2016](#)). A quantitative bias analysis will assess the impact of residual confounding on the observed results.

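### The bias analysis for malformations missed in non-live births is aimed at MCM prevalence and does not commit to the primary MCM relative risk or to loss that differs by cohort

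*Protocol*

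**What the plan says.** - **Where MCM is scored.** Protocol 7.2.1.1.3 says that identifying infant outcomes "relies on data from the infant's claims record rather than the mother's claims record". Section 7.10 adds: "MCMs will be identified in live born infants, and study drug exposure will be assessed in the first trimester". Section 7.7.3.2 accepts that infant outcomes are confined to pregnancies with a linked infant.
- **The primary comparison.** Section 7.7.3.3: "we will estimate RRs comparing the Nemolizumab Cohort to the comparator cohorts using robust Poisson regression models", for MCM and small-for-gestational-age birth, with stabilised weights. Under 7.7.3.1 the propensity score uses only information from cohort entry or earlier.
- **The planned bias analysis.** Section 7.7.3.5.8 first plans to quantify MCMs that the main analysis may have missed because the pregnancy was terminated, miscarried or stillborn. It then states the purpose of the bias analysis: to "evaluate the impact of elective termination, spontaneous abortion, and stillbirth on prevalence estimates for MCM".
- **The neighbouring bias analyses.** Section 7.7.3.5.6 (unmeasured confounding) is aimed at the observed RRs. Section 7.7.3.5.7 (outcome misclassification) is aimed at the comparative analyses and mentions differential error. Section 7.7.3.5.8 mentions neither the RR nor differential loss.

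**The concern.** A pregnancy that ends in termination, spontaneous abortion or stillbirth has no MCM score. If affected pregnancies are lost in this way at the same rate in every cohort, the prevalences are too low but their ratio hardly changes. If the rate differs, the RR among live births is biased. For example, if women on a new drug were followed more closely before birth and affected pregnancies were more often ended, affected cases would leave the exposed numerator and the RR would fall. The opposite pattern would raise it.

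The RR is the comparative estimate for the primary outcome. Weighting on covariates up to cohort entry cannot correct selection that happens later. A bias analysis that reports only how far prevalence is understated would leave open whether the RR could have been moved.

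**Working it through.** **1. The plan's own figures.** Inputs from section 7.5 and Table 3: comparator MCM prevalence 3%; "assuming a ratio of 1:4 exposed to unexposed, 80% power, a 2-sided alpha of 0.05"; for an RR of 2.5, "a study size of 214 live births with linked infants exposed to nemolizumab in the first trimester exposure window would provide an 80% power"; "Assuming 80% of pregnancies have an observed outcome and 76% of observed outcomes are live births".

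Fleiss formula without continuity correction, with p0 = 0.03, p1 = 0.075, r = 4 and pooled p = (0.075 + 4 × 0.03)/5 = 0.039:

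n = [1.960 × √(1.25 × 0.039 × 0.961) + 0.842 × √(0.075 × 0.925 + 0.03 × 0.97/4)]² / 0.045² ≈ 213.3, rounded up to **214**. This agrees with the plan.

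214/(0.80 × 0.76) = 351.97, so **352**. This also agrees: "an estimated 352 pregnancies exposed to nemolizumab during the first trimester would need to be accrued to detect a RR of 2.5".

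**2. How many exposed pregnancies end in an observed non-live birth.** 352 × 0.80 × (1 − 0.76) = 67.6, about **68**, or 68/352 = 19%. Table 3's separate prevalences for termination (21%), spontaneous abortion (14%), stillbirth (1%) and ectopic pregnancy (1–2%) add to 37–38% rather than 24%, so 68 may be low. The point does not depend on this.

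**3. Effect on the RR.** Let q0 and q1 be the probabilities that an affected pregnancy ends before live birth in the comparator and exposed cohorts. With unaffected pregnancies alike in both cohorts and MCM uncommon:

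observed RR ≈ true RR × (1 − q1)/(1 − q0).

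The documents give no value for q0 or q1. Those below are assumptions, with q0 = 0.20:

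| q1 | (1 − q1)/(1 − q0) | true RR 2.5 seen as | true RR 1.0 seen as |
|---|---|---|---|
| 0.10 | 1.125 | 2.81 | 1.13 |
| 0.20 | 1.000 | 2.50 | 1.00 |
| 0.30 | 0.875 | 2.19 | 0.88 |
| 0.40 | 0.750 | 1.88 | 0.75 |
| 0.50 | 0.625 | 1.56 | 0.63 |

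**4. Check with the live-birth denominators kept.** Let s be the probability that an affected pregnancy reaches live birth, and L = 0.76 the same for an unaffected one (the protocol's overall share, borrowed here). Then:

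prevalence among live births = p·s / [p·s + (1 − p)·L].

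Take s0 = 0.60 (assumed), with comparator live-birth prevalence fixed at 3%, so that p0 = 0.0377 and, for a true RR of 2.5, p1 = 0.0942:

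| s1 (assumed) | observed RR | power with 214 exposed live births |
|---|---|---|
| 0.70 | 2.92 | 91% |
| 0.60 | 2.53 | 81% |
| 0.50 | 2.14 | 63% |
| 0.40 | 1.73 | 37% |
| 0.30 | 1.32 | 12% |

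Equal loss leaves the RR almost unchanged (2.53 against 2.5). Unequal loss moves it in either direction.

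**5. A tipping point.** For an observed RR of 1.0 to conceal a true RR of 2.5, (1 − q1)/(1 − q0) must equal 0.4. With q0 = 0.20, q1 = 1 − 0.4 × 0.80 = 0.68, a difference of 48 percentage points. A reader could judge whether such a difference is plausible, and the plan does not promise this figure.

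**6. Do the observed non-live-birth frequencies limit q?** No. If 24% of pregnancies end in a non-live birth and 3% or 7.5% are affected, the implied ceilings are 0.24/0.03 = 8 and 0.24/0.075 = 3.2. Both exceed 1, so every affected pregnancy could in principle be lost.

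**The case against.** The case for the protocol is substantial.

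- **The bias is recognised.** Section 7.7.3.5.8 names the three routes of loss, and its opening sentence refers to the main analysis without restricting itself to prevalence.
- **MCM frequency is reported by cohort.** The second objective in section 6 asks for it in all three cohorts, and 7.7.3.2 gives prevalence before and after weighting. If the bias analysis is run by cohort, dividing two corrected prevalences gives a corrected RR.
- **Indirect evidence is collected.** Section 7.7.3.3 compares termination, spontaneous abortion and stillbirth between cohorts by hazard ratio. Section 7.4.3.6 records prenatal visits, amniocentesis, ultrasound and screening. Section 7.10 describes censoring by exposure.
- **The grid and reporting scale are commonly left to the SAP**, which is not shown.
- **One comparator is other monoclonal antibodies for the same diseases**, and the documents give no reason to expect a large difference in loss against that group.

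Much of this stands. A reader might infer that live-birth selection is ignored, or that the RR can never be examined for it. The documents do not support that, because the material for a corrected RR would largely be available. What remains is that the protocol states the target of this analysis and stops at prevalence, although the two sections before it name the comparison. The hazard ratios cover all pregnancies rather than affected ones, the prenatal markers are descriptive only, and none of this is carried into the MCM RR.

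**Conclusion.** The point holds as a gap in the stated scope of one planned analysis. Section 7.7.3.5.8 addresses MCM prevalence and commits neither to the RR for the primary outcome nor to loss that differs by cohort, the form of loss that threatens the RR.

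About 68 of 352 exposed pregnancies (19%) are affected by this route on the protocol's planning shares. The RRs in the tables show sensitivity to assumed loss probabilities and do not estimate actual bias. Its size and direction are unknown.

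Two stronger readings should be resisted. A reader might infer that the study will hide a teratogenic effect, but that requires greater loss of affected pregnancies in the exposed cohort, which nothing in the documents establishes. A reader might also multiply 0.80 × 0.76 × 0.85 and conclude that only 52% of exposed pregnancies can be scored because of live-birth selection. That product mixes in pregnancies without an observed outcome and unlinked infants, which are separate problems, and section 7.5 leaves unclear whether the 85% linkage rate (7.2.1.1) is an additional factor.

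**What to change.** In 7.7.3.5.8, extend the target of the bias analysis so that it reads: on the prevalence estimates and on the RR for MCM versus each comparator. Then state that:

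- the probability that an affected pregnancy ends before live birth is varied separately in each cohort, in both directions, over a stated assumed range;
- the observed frequencies of termination, spontaneous abortion and stillbirth may inform that range but do not bound it;
- the report gives the corrected RRs and the between-cohort difference in loss needed to move the RR to 1 and to 2.5.

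This follows the rule-out reasoning already adopted in 7.7.3.5.6 and needs no new data. The cost is one more table. Its drawback is that it rests on parameters the study cannot observe, as the planned prevalence analysis already does.

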7.7.3.5.9 Sensitivity Analysis Applying European Union (EU) Definitions of Adverse Pregnancy Outcomes

This study uses US databases and US definitions of adverse pregnancy outcomes based on ICD-10-CM codes. However, EU definitions of adverse pregnancy outcomes are slightly different, as early foetal death (before 22 completed weeks of gestation) is known as miscarriage, whereas late foetal death (after 22 completed weeks of gestation) is known as stillbirth. In this sensitivity analysis, we will reclassify pregnancies with a code for stillbirth prior to 22 completed weeks gestation as miscarriage and repeat the analyses for these two outcomes.

7.7.4 Missing Data

This study is based on an analysis of automated medical and prescription claims. Data collected for administrative purposes, such as age (or date of birth) and sex, are not expected to be missing, and records with this information missing will not be used for analysis.

Using the standard approach in claims data analyses, the presence of a medication or diagnosis claim will be assumed to indicate use of that medication or the presence of that condition. Conversely, the absence of a medication or diagnosis claim will indicate the absence of use of that medication or a diagnosis of the condition. Therefore, covariates related to drug use and disease status will be categorized as yes (code present) or no (no code present) and there will be no missing data for these variables.

Within Optum's Market Clarity, an integrated claims-EHR data source, clinical variables are missing for some individuals because of variation in care practices. Health care encounters with medical providers who do not contract with Optum will not be observed. Because the EHR database is an open system, some patients may only receive a fraction of their care through a provider captured in the data, and medical encounters outside of the networks contributing data to the EHR database will not be observed. To mitigate the potential for missingness in the data, we will require that the study cohorts have evidence of routine care (i.e., at least one outpatient visit at least 6 months prior to the index date) within the contributing EHR systems. Patients meeting this criterion likely have a reasonably high capture of medical encounters in the data. Additionally, the EHR data in Optum's Market Clarity are supplemented with medical and pharmacy claims, likely improving the capture of clinical variables for most patients.

7.8 Quality Control

7.8.1 Research Partner Sites

Each research partner site will follow a common protocol and SAP. Additionally, within each research partner site, Standard Operating Procedures (SOPs) or similar guidelines will be used for the conduct and reporting of the study. These procedures will include internal quality audits, rules for secure and confidential data, methods to maintain and archive project documents, quality control procedures for programming, and requirements for additional review and oversight throughout the project duration.

The protocol will be updated to incorporate other research partners and descriptions of their site-specific quality control measures.

7.8.2 Optum

Optum is responsible for site-specific analyses (annual counts, feasibility report, final report) as well as combining results from all research partner sites (annual counts starting in 2030 and final report). The conduct and reporting of this study follows Optum Epidemiology's SOPs that are consistent with the International Society for Pharmacoepidemiology (ISPE)'s Guidelines for Good Pharmacoepidemiology Practices (GPP) (ISPE, 2015) as well as The European Network of Centres for Pharmacoepidemiology and Pharmacovigilance (ENCePP): Guide on Methodological Standards in Pharmacoepidemiology and the EMA Guideline on Good Pharmacovigilance Practices: Module VIII – Post-authorization Safety Studies. For pregnancy safety studies such as this, the suggested study design and methodology are consistent with the FDA draft guidance document Postapproval Pregnancy Safety Studies Guidance for Industry (<https://www.fda.gov/regulatory-information/search-fda-guidance-documents/postapproval-pregnancy-safety-studies-guidance-industry>). In particular, the SOPs in place at Optum prescribe that processes and deliverables are documented, reviewed, and validated in sufficient detail to allow for subsequent re-examination or replication.

The validation of analytic work typically involves a combination of a review of program logs and lists, independent coding, a review of program processes and documentation to ensure Optum SOPs are followed, and reconciliation of program code with the study protocol to ensure populations and results are consistent with what is needed for the study. Individual programs are documented and revised as needed until sign-off by a validation analyst using the validation/programming log.

The validity of the ORD for epidemiologic research (as compared with data abstracted from medical records) has been established (Dore et al., 2011; Eng et al., 2012; Loughlin et al., 2010).

7.9 Adverse Event Reporting

According to the EMA Guideline on Good Pharmacovigilance Practice: Module VI, there is no requirement for reporting of adverse drug reactions from secondary use of data such as electronic health care databases. In these data sources, it is not possible to identify a potential association between a particular product and medical event for any individual. Thus, the minimum criteria for reporting an adverse event (identifiable patient, identifiable reporter, a suspect product, and event) cannot be met. Only aggregated safety results describing the overall association between an exposure and an outcome will be summarized in the study reports.

7.10 Limitations of the Research Methods

This proposed study is based on an analysis of claims and EHR databases. While these data sources are valuable, they have certain limitations because they are collected for the purpose of payment and patient management, not research. The presence of a claim for a filled prescription does not indicate that the medication was consumed or that it was taken as prescribed. Medications filled over the counter or provided as samples by the physician will not be observed in the claims data,

although this information may be available for some patients in the free-text clinical notes within Optum's Market Clarity database. The presence of a diagnosis code is not confirmation of disease, as the diagnosis code may be incorrectly coded or included as rule-out criteria rather than actual disease. Duration of follow-up can be limited in the claims data due to individuals changing health insurance plans.

The study power will be limited until several years of cohort accrual have passed. Because accrual of nemolizumab initiators depends on actual use within the insured population that is the source for the study, divergence in numbers of users from sample size projections might affect how rapidly the study power reaches an adequate level.

While there are validated algorithms for moderate to severe AD and for PN ([Chomistek et al., 2023a](#); [Roh et al., 2022](#)), there is currently no published algorithm for moderate to severe PN. The overall PN algorithm may lead to the inclusion of mild PN cases in our study population. During the study period, published literature will be searched for a validated claims-based algorithm to identify moderate to severe PN. If a validated algorithm is found that has suitable performance characteristics, the methods for identifying PN may be modified.

MCMs will be identified in live born infants, and study drug exposure will be assessed in the first trimester. However, the exact timing of the development of malformations is typically unknown. Additionally, while the use of ICD-10-CM Z3A codes to estimate LMP has been shown to be accurate ([Chomistek et al., 2023b](#)), not all pregnancies have Z3A codes, and some degree of measurement error is expected in estimating the beginning of pregnancy. The resulting exposure misclassification due to estimated LMP is not expected to be differential with respect to exposure. A sensitivity analysis will explore alternative exposure windows that are more conservative.

It is possible that selection bias may arise due to differential loss to follow-up (i.e., if pregnant women who receive nemolizumab are more or less likely to be lost to follow-up than those who are exposed to other AD/PN treatments or who are unexposed), though we expect censoring to be non-differential with respect to exposure and outcome status. To check this assumption, we will compare the baseline characteristics of pregnancies with an observed outcome versus those who were censored before the end of pregnancy. We will also describe the frequency of censoring events according to nemolizumab exposure status.

Residual confounding is always a concern in observational studies. While propensity score models can account for a large number of measured pre-specified and empirically derived variables, some variables may have a greater degree of misclassification, and some confounders may not be measured. For example, due to ICD-10 coding limitations, claims data tend to have incomplete capture of smoking status. However, the degree of residual confounding due to unmeasured factors may be reduced if proxies of unmeasured factors are included in the models ([Guertin et al., 2016](#)). A quantitative bias analysis will assess the impact of residual confounding on the observed results.

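### Loss to follow-up and non-linkage are checked only descriptively, so differing loss patterns between cohorts can bias the HRs and RRs, and even identical patterns can bias the frequency estimates

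*Protocol*

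**What the plan says.** Section 7.5 of the protocol derives the target number of pregnancies from two assumptions: "Assuming 80% of pregnancies have an observed outcome and 76% of observed outcomes are live births". Section 7.2.1.1 puts mother-infant linkage in the Optum Research Database at about 85% of live-birth pregnancies.

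Section 7.10 raises differential loss as a possible source of selection bias and sets it aside: "though we expect censoring to be non-differential with respect to exposure and outcome status". It plans two checks. The first is "To check this assumption, we will compare the baseline characteristics of pregnancies with an observed outcome versus those who were censored", meaning those lost while still pregnant. The second describes how often censoring occurs by nemolizumab exposure. Section 7.7.3.2 adds a third, for infant outcomes: mothers of linked infants against mothers of non-linked infants. None is stated to be made within each cohort, and no analysis or action follows from any of them.

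The weights serve another purpose: "All comparative analyses will be performed incorporating stabilized IPTW to adjust for potential confounding" (7.7.3.3). Under 7.7.3.1 they target the average treatment effect in the treated (ATT), use covariates known by cohort entry, and come from two propensity score models in total. None of the nine sensitivity analyses in 7.7.3.5 deals with loss. The three quantitative bias analyses cover unmeasured confounding, outcome misclassification, and malformations missed in pregnancies that did not end in live birth.

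**The concern.** Weighting at cohort entry balances the cohorts as they start. It does not keep them balanced among the pregnancies whose outcome is seen or whose infant is linked. If women with a risk factor leave one cohort more readily than the other, the retained groups differ even though the weighted cohorts did not.

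Different patterns are possible here. Censoring is by disenrolment or, in data with health records, by eight weeks without clinical activity (Table 2). The latter depends on contact with care, which may differ between biologic-treated and unexposed women. Section 7.2.1.1.3 attributes some non-linkage to mothers insured on their own parents' policy.

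At stake are the comparative estimates, including the primary outcome, major congenital malformation (MCM), and separately the absolute frequencies.

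**Working it through.** **1. The plan's own figures.** Inputs from 7.5: MCM prevalence 3%, "assuming a ratio of 1:4 exposed to unexposed, 80% power, a 2-sided alpha of 0.05". The Fleiss formula without continuity correction gives 214 live births for RR 2.5 and 133 for RR 3, as stated. Then 214/(0.80 × 0.76) = 351.97, so 352, and 133/0.608 = 218.75, so 219. Both match. The 20% is therefore built into the target: 352 × 0.20 = 70 exposed pregnancies. For infant outcomes linkage comes on top: 0.80 × 0.85 = 0.68 of live-birth pregnancies would reach the analysis, if the 80% applies equally to live births.

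**2. When the RR is biased.** Assumptions, not in the protocol: one binary baseline risk factor L, prevalence 30% in both cohorts after weighting, multiplying risk by k = 2 or 3; total loss 20% in each cohort. The retained share with L is s = 0.30 × (1 − loss with L)/0.80, and the retained risk is proportional to 1 + (k − 1)s.

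- Pattern A: loss 43.3% with L, 10% without; s = 0.2125
- Flat: 20% and 20%; s = 0.300
- Pattern B: 5% and 26.4%; s = 0.356
- Pattern C: 14.2% and 22.5%; s = 0.322

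Results at a true null (HRs from the large-sample Cox score equation, constant hazards over 18 weeks, outcome risk 2% or 14%):

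| Exposed / comparator | RR, k = 2 | RR, k = 3 | HR, k = 2 | HR, k = 3 |
|---|---|---|---|---|
| A / A | 1.00 | 1.00 | 1.00 | 1.00 |
| A / flat | 1.2125/1.300 = 0.93 | 1.425/1.600 = 0.89 | 0.97 | 0.95 |
| A / B | 1.2125/1.356 = 0.89 | 1.425/1.7125 = 0.83 | 0.95 | 0.92 |
| A / C | 1.2125/1.322 = 0.92 | 1.425/1.644 = 0.87 | not run | not run |

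With a milder exposed pattern (31.7% with L, 15% without) against flat loss, the RR is 0.97 or 0.95. Exchanging the cohorts inverts the null RRs: 1/0.89 = 1.12 and 1/0.83 = 1.20.

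**3. Same pattern, true effect present.** Under A / A with a constant RR of 2.5, the retained RR is 2.5. The HR moves by under 0.5% (for example 2.418 to 2.429 at 14% risk, k = 3). If instead the RR is 1.5 without L and 3.0 with L:

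- k = 2: the ATT is (0.70 × 1.5 + 0.30 × 2 × 3)/1.30 = 2.19; the retained value is (0.7875 × 1.5 + 0.2125 × 2 × 3)/1.2125 = 2.03.
- k = 3: 3.75/1.60 = 2.34 against 3.094/1.425 = 2.17.

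**4. Frequencies.** Under pattern A with k = 3 and a 2.5% risk without L, the true prevalence is 0.025 × 1.60 = 4.0% and the retained prevalence is 0.025 × 1.425 = 3.6%, whichever pattern the other cohort follows.

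**5. Would the 7.10 checks show it?** Take A / C at 1:4. Comparator loss is 0.30 × 0.142 + 0.70 × 0.225 = 20%, equal to exposed loss, so the frequency check shows no difference. Pooled loss with L is 0.2 × 0.433 + 0.8 × 0.142 = 20%; without L it is 0.2 × 0.10 + 0.8 × 0.225 = 20%. The pooled baseline comparison also shows no difference, while the null RR is 0.92 or 0.87. This is a constructed exact cancellation. It shows that the checks do not test the condition that matters, namely whether loss depends on covariates differently by cohort.

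**The case against.** **Direction and size are assumed.** The protocol gives no data on who is lost. The main scenarios use a steep gradient in one cohort and a flat or reversed one in the other. The active comparators are also injectable biologics, and matching is within data source, which makes sharply different patterns less likely for that contrast. This stands: the figures are illustrations.

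**The bias is small beside the planned precision.** With 214 exposed and 856 comparator infants at 3%, SE(log RR) = √(0.97/6.42 + 0.97/25.68) = 0.43, so the 95% interval spans a factor of about exp(1.96 × 0.43) = 2.3 each way. The largest bias above, ln 0.83 = −0.19, is under half a standard error. This also stands, and it limits the severity.

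**The 20% is not all loss to follow-up.** Section 7.5 does not split it by cause, and it may include pregnancies cut off by the end of the study, which is administrative. This stands.

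**Covariates imbalanced by 0.1 or more enter the outcome model.** That would help if balance were judged among retained pregnancies or linked infants. Section 7.7.3.1 speaks only of balance between the cohorts before and after weighting.

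**This may belong in the SAP.** The SAP is not shown and could add censoring weights. But the protocol expressly defers other items to it and not this one. It states its own check of its own assumption, and that check misses the relevant condition.

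**Conclusion.** The point holds in a limited form. Loss after cohort entry is assumed harmless and examined only descriptively, and the treatment weights do not correct it. Comparative estimates can be biased if the covariate pattern of loss differs between cohorts (about 3% to 17% on the RR in the scenarios tried) or if the effect varies over the covariates that drive loss (2.03 against 2.19 and 2.17 against 2.34). Frequencies can be biased under identical patterns (3.6% against 4.0%). All these sizes rest on the assumed inputs above.

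A reader might infer that any covariate-dependent loss biases the HRs and RRs even when it acts alike in both cohorts. It does not: with the same pattern and a constant effect the RR is unbiased, and the HR is exact at the null and nearly so elsewhere. A reader might also infer that the bias would hide harm. Nothing in the protocol fixes its direction; exchanging the cohorts reverses it.

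**What to change.** 1. In 7.10 and 7.7.3.2, compare censored with observed pregnancies, and linked with non-linked ones, within each cohort.
2. In 7.7.3.5, add a sensitivity analysis reported beside the main result. For the Cox models and incidence estimates, multiply the ATT weights by stabilised inverse probability of censoring weights. For MCM and small-for-gestational-age birth, multiply them by the inverse of the modelled probability of being both observed and linked. Use a small set of baseline covariates with exposure interactions, truncate the weights, and treat end-of-study censoring as administrative.

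The covariate set must be small: about 70 exposed pregnancies are expected without an outcome, spread over databases analysed separately. For the same reason this is proposed as a sensitivity analysis and not as the main one. The cost is protocol wording, programming and somewhat wider intervals in that analysis; no new data are needed. The weights correct only for measured covariates, so loss related to the outcome beyond them would remain.
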